Primary objective: To conduct an RCT that examines the efficacy of e-Motivate versus a control condition for increasing screening colonoscopy uptake in Black/African Americans. Black/African American patients referred for a screening colonoscopy will be recruited to the RCT. Participants (N=200) will be randomly assigned to an e-Motivate group (N=100) or a control group (N=100). Participants in e-Motivate group will receive usual care and will also complete a one-time, 20-minute e-Motivate app on a tablet immediately following the primary care appointment in which they received a referral for a screening colonoscopy. Participants in the control group will receive usual care (e.g., print handout, patient navigation). It is hypothesized that participants in e-Motivate condition will be more likely to complete the recommended screening colonoscopy.

 Mount Sinai	Protocol Name:	Internet-based Motivational Interviewing for Colonoscopy in African Americans
	Principal Investigator:	[name]
	Primary Contact Name/Contact Info:	[name], [contact] ,
	Date Revised:	8/16/19
	Study Number:	GCO# 14-0275 IF# HS#

Exploratory Aim 2a. To explore the efficacy of e-Motivate for improving a secondary adherence outcome (e.g., bowel prep quality).

Exploratory Aim 2b. To explore mediators and moderators of e-Motivate. As a part of the RCT, potential mediators (i.e., competence, autonomy, relatedness) and moderators (i.e., demographics, Internet fluency/use) will be explored.

2) Background

Colorectal cancer (CRC), a largely preventable disease, remains the second cause of cancer death in the United States in men and women combined. Compared to other racial groups, Black/African Americans have the highest CRC morbidity and mortality rates. Given these disparities, it is critical to increase Black/African Americans' participation in CRC prevention efforts.

A motivational interviewing (MI) intervention can help improve Black/African Americans' screening colonoscopy uptake. MI is a brief patient-centered intervention that increases perceived competence, autonomy, and relatedness in order to promote behavioral change. Extensive research supports the efficacy of MI to promote preventive health screening uptake (e.g., increase HIV testing) and MI has proven efficacious with Black/African Americans across a wide range of diseases. There is strong support for the use of MI to improve Black/African Americans' screening colonoscopy uptake.

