Traditionally, MI is delivered live, where individuals meet with a professional for a one-on-one intervention. Although efficacious, live-MI is not without limitations. Of greatest concern, live-MI requires both staffing and economic resources, limiting its ability to be widely disseminated. A motivational interviewing based app (called e-Motivate) may overcome these limitations. By eliminating the need for an on-site professional, e-Motivate is a high reach, low cost intervention with the potential to have a significant public health impact. Research with other health behaviors supports the efficacy of electronically delivered MI. Yet, no research to date has examined the efficacy of e-Motivate to increase screening colonoscopy uptake in Black/African American patients.

3) Setting of the Human Research

The research will be conducted at Mount Sinai Hospital (IMA and GI clinic) and Mount Sinai Doctors West 147th Street. Patients will be recruited immediately following their primary care or GI appointment in which they received a referral for screening colonoscopy.

4) Resources Available to Conduct the Human Research

 Mount Sinai	Protocol Name:	Internet-based Motivational Interviewing for Colonoscopy in African Americans
	Principal Investigator:	[name]
	Primary Contact Name/Contact Info:	[name], [contact] ,
	Date Revised:	8/16/19
	Study Number:	GCO# 14-0275 IF# HS#

The IMA clinic sees over 25,000 unique clients annually of whom, 37.3% are African American. The total target population of 240 is therefore feasible. Mount Sinai Doctors West 147th street is located in Harlem and treats a predominantly racial/ethnic minority patient population.

As a part of the agreement to abide by regulations set forth by the Mount Sinai Institutional Review Board all members of the research team have been trained in all aspects of the protocol, Human Subjects Protection and HIPAA requirements.

5) Study Design

a) Recruitment Methods

Patients will be recruited from the Mount Sinai Hospital (IMA and GI clinic) and Mount Sinai Doctors West 147th Street immediately following an appointment with their physician. The physician or patient navigator will provide a brief description of the study to the patient. If the patient is interested in learning more about the study, he/she will meet with the Research Assistant (RA) in a private room immediately following their GI or PCP appointment to review the study and complete the consent form.

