If the patient is interested in participating in the study, but unable to complete the study after the clinic visit (e.g., time constraints, first contact with patient navigator is over the telephone, RA is not on site), the patient can provide the healthcare professional (physician or patient navigator) with permission to be contacted by the study research team. The healthcare provider (e.g., patient navigator or physician) will then give the research staff the patient's preferred contact information. The research staff members will then contact the patient to arrange for a convenient time to meet to complete the consent and intervention.

b) Inclusion and Exclusion Criteria

Eligibility criteria include: 1) self-identify as Black/African American; 2) received a referral for a screening colonoscopy; and 3) English speaking

Healthcare providers (e.g., primary care physicians and gastroenterologists) will determine whether the patient is medically eligible for a screening colonoscopy (e.g., age eligible for a screening colonoscopy based on published guidelines).

Exclusion include: 1) hearing or vision impaired; 2) Phase I participant

c) Number of Subjects

200 participants (100 per condition)

d) Study Timelines

The total study duration is 5 years (September 2015-October 2020).

Years 1-2: Create and field test e-Motivate

Years 3-4: Enroll participants in RCT (Phase II)

 Mount Sinai	Protocol Name:	Internet-based Motivational Interviewing for Colonoscopy in African Americans
	Principal Investigator:	[name]
	Primary Contact Name/Contact Info:	[name], [contact] ,
	Date Revised:	8/16/19
	Study Number:	GCO# 14-0275 IF# HS#

Years 4-5: Conduct follow up medical chart reviews. Conduct qualitative follow up interviews. Conduct all data analyses.

e) Endpoints

Participants in the RCT will have their medical charts reviewed, six months following the initial referral, to determine if the colonoscopy has been completed. Secondary outcomes (e.g., bowel prep quality, number of cancellations) will also be recorded. Participants will also complete a demographics assessment and a questionnaire that assesses mediators (autonomy, competence, relatedness).

There are no events/results that would cause a study subject's participation to end due to safety.

f) Procedures Involved in the Human Research

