each recruitment day, the RAs will use the CERNER list and EMR to review patients' race, age, and previous colonoscopy history. RAs will alert healthcare providers (e.g., physicians and patient navigators) daily of patients who may be eligible for a screening colonoscopy referral. If a patient is eligible for the study (e.g., self-identifies as black/African American, age-eligible for CRC screening, and received a referral for a screening colonoscopy), the physician or patient navigator will briefly introduce the study to the patients at the end of the primary care or GI appointment. Patients who are interested in participating in the study will meet with an RA in a private exam room immediately following their appointment to review and complete the consent form.

If the patient is interested in participating in the study, but unable to complete the study after the clinic visit (e.g., time constraints, first contact with patient navigator is over the telephone, RA is not on site), the patient can provide the healthcare professional (physician or patient navigator) with permission to be contacted by the study research team. The healthcare provider (patient navigator or physician) will then give the research staff the patient's preferred contact information. The research coordinator will then contact the potential participant and schedule a date/time to complete the consent form.

Consented participants will complete a verbally administered baseline questionnaire. Participants will then be assigned to one of two groups: e-Motivate (N=100) or control group (N=100). Participants assigned to e-Motivate condition will receive usual care and will also complete the 20 minute e-Motivate app. Immediately after completing the e-Motivate app, the RA will verbally administer a post-intervention questionnaire that assesses the hypothesized mediators. Participants in the control group will receive usual care (e.g., patient navigation, print materials). Participants will receive \$20 gift card to Target as compensation. Six months following the initial referral, medical charts will be reviewed to determine whether the colonoscopy was completed, the quality of the bowel prep, and process variables (e.g., number of cancellations/rescheduled appointments/no-shows)

g) Specimen Banking

N/A

h) Data Management and Confidentiality

Survey Data:

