Missing data: The e-Motivate is a one-time intervention and thus we anticipate minimal missing data. *Analyses of covariates:* Participants will be randomly assigned to treatment condition and therefore significant baseline differences are not expected. However, contingency tables and t-tests will be performed to determine any differences between the two groups. Using a p value of ≤ 0.15 , any consistent pattern of correlation for any of the covariates would suggest their inclusion in the primary data analysis model.

Analysis of Primary Outcome: The primary outcome (screening uptake) will be assessed with a logistic regression model. The hypothesized moderators will be evaluated individually. The final logistic model will contain the main effect for the treatment group, any identified covariates, and any significant moderators.

Analysis of Secondary Outcome: If bowel prep quality is normally distributed, a t-test will be used to compare the two treatment groups.

Exploration of Mediation: In the mediation analyses, we will first show that treatment predicts the primary outcome. We will next evaluate the extent to which the treatment affects the mediators using a linear mixed model with repeated measures. Time will be entered into the model first followed by any covariates. Next, the binary treatment vector will be introduced as a main effect followed by interaction with time. Since there are three

 Mount Sinai	Protocol Name:	Internet-based Motivational Interviewing for Colonoscopy in African Americans
	Principal Investigator:	[name]
	Primary Contact Name/Contact Info:	[name], [contact] ,
	Date Revised:	8/16/19
	Study Number:	GCO# 14-0275 IF# HS#

correlated mediators, the p-values will be adjusted using the Sidak correction for multiple comparisons. Only the mediators that are predicted by the treatment main effect or the time by treatment interaction will be retained. Each mediator will then be introduced into the logistic model predicting the primary outcome. To establish mediation, the indirect paths from treatment to mediators and from mediators to outcomes will be assessed using 1000 bootstrap samples following the procedures.

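### Referral setting (primary care or GI) is known before assignment but reaches the primary model only through a p ≤ 0.15 screen; make it a fixed term and align the objective's timing sentence.

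*Combined protocol and SAP*

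**What the plan says.** **Where participants come from.** Section 1 (Objectives) has the e-Motivate arm complete the app "on a tablet immediately following the primary care appointment in which they received a referral for a screening colonoscopy". Section 3 (Setting) says: "Patients will be recruited immediately following their primary care or GI appointment in which they received a referral for screening colonoscopy". It names three recruitment points: the IMA clinic, the GI clinic and Mount Sinai Doctors West 147th Street. Under RCT Procedures, section 5f has the physician or navigator, who "will briefly introduce the study to the patients at the end of the primary care or GI appointment", do so on both routes.

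**Who is eligible.** The objective's recruitment sentence carries no clinic limit: "Black/African American patients referred for a screening colonoscopy will be recruited to the RCT". Section 5b requires a referral but does not make referral setting a criterion.

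**Assignment.** Sections 1 and 5h say assignment is random, and section 5f gives 100 per group. No method, blocking or stratification factor is stated.

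**Adjustment.** Section 5h (Data Analyses) compares the two groups with contingency tables and t-tests, then says: "Using a p value of ≤ 0.15 , any consistent pattern of correlation for any of the covariates would suggest their inclusion" in the primary model. The final logistic model holds treatment, any covariates so identified and any significant moderators. Setting is named neither as a covariate nor among the moderators in Exploratory Aim 2b (demographics and Internet fluency/use).

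**Power.** Section 5h uses one pooled rate per arm, 71.4% and 52.0%, with none by setting.

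**The concern.** A GI-clinic recruit is already in contact with a gastroenterology service when enrolled; a primary care recruit may not be. It is reasonable to expect uptake to differ between them, although the documents do not say so. The trial knows each participant's setting before assignment, at no cost.

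The plan leaves use of that information to a screen. The natural reading is that the screen looks for baseline differences between arms, because it follows directly on the group comparisons. Under randomisation such differences arise by chance. The screen therefore keeps setting when the arms happen to differ and drops it when they do not, however strongly setting predicts completion. At stake are some precision in the primary comparison and any planned view of results by setting. Separately, the objective and the procedures disagree about the visit after which the app is given.

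**Working it through.** **1. The plan's power.** Inputs from Analysis of Power: 100 per arm, 71.4% vs 52.0%, alpha 0.05 (two-sided assumed; sidedness is not stated).
- Difference 0.194; mean rate 0.617.
- Null SE = √(2 × 0.617 × 0.383 / 100) = 0.0687.
- Alternative SE = √((0.714 × 0.286 + 0.52 × 0.48) / 100) = 0.0674.
- Power = Φ((0.194 − 1.96 × 0.0687) / 0.0674) = Φ(0.88) = 0.81. The unpooled version gives 0.82.

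The stated 0.83 is reproduced within 2 points.

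**2. Assumptions.** The documents give no GI share and no uptake by setting. Assumed: GI share 40-50%; control uptake higher after a GI visit by 10 to 40 points; overall rates held at 52% and 71.4%; the same odds ratio in both settings. At 50% GI and a 40-point gap, control uptake would be 32% in primary care and 72% in GI, which is extreme.

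**3. What the screen catches.** For GI share s, the SD of the arm difference in GI share is √(2s(1 − s)/100): 0.069 at s = 0.4 and 0.071 at s = 0.5.
- 95% range: 1.96 × SD = about ±14 points.
- Flagged at p ≤ 0.15: 1.44 × SD = about 10 points or more.
- Largest unflagged shift in the uptake difference: about 10 points × gap, so about 2 points at a gap of 0.2 and 4 points at 0.4.

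These shifts are chance and already lie within the sampling error of the difference, whose 95% half-width is 1.96 × 0.0674 = about 13 points.

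**4. Power by analysis rule.** Simulated trials of 200 participants, 8,000 per scenario:

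| GI share, gap | p ≤ 0.15 imbalance screen | Always adjust | Stratify and adjust |
|---|---|---|---|
| 40%, 20 points | 0.815 | 0.825 | 0.824 |
| 40%, 30 points | 0.815 | 0.832 | 0.837 |
| 50%, 40 points | 0.823 | 0.864 | 0.861 |

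The gains from always adjusting over the screen are 0.010, 0.017 and 0.041. At a 10-point gap there is none. The simulation SE of each entry is about √(0.82 × 0.18 / 8,000) = 0.004, so the smallest gain should be read only as roughly 1 point. Type I error is about 0.04-0.06 under either rule. Stratification adds essentially nothing beyond the fixed term.

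**5. Can the trial show a difference by setting?** Suppose the effect is 19.4 points in primary care and 0 in GI. With v = 0.714 × 0.286 + 0.52 × 0.48 = 0.454, the interaction SE is √(v/(100f) + v/(100(1 − f))) for GI share f. Power is Φ(0.194/SE − 1.96) = 0.14, 0.24 and 0.30 at f = 10%, 25% and 50%. By-setting results can only be descriptive.

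**6. Cost on the odds ratio scale.** The marginal odds ratio is (0.714/0.286)/(0.52/0.48) = 2.30. With 50% GI and a 30-point gap, the conditional one is 2.49.

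**The case against.** **The screen may already do the job.** Section 5h does not say what the covariates should correlate with. If it means the outcome, setting would be kept for prognostic strength, and power is 0.824, 0.832 and 0.864 in the three scenarios, the same as always adjusting. This stands as a reason to state the rule, but the adjacent group comparisons favour the between-arm reading.

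**The size is small and rests on assumptions.** This stands. No input on setting comes from the documents. Comparing always adjusting with no adjustment at all would overstate the gain, because the plan does adjust for the larger imbalances.

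**Stronger readings that the documents do not support:**
- *GI recruits are at a later step towards colonoscopy.* A reader might infer this, but section 3 puts both groups at the appointment where the referral was given, and section 5e counts six months from the initial referral for everyone.
- *The objective's population is primary care.* Only its sentence on app timing is so limited; its recruitment sentence covers any referred patient.
- *Pooling or imbalance biases the result.* Random assignment keeps the comparison unbiased in expectation, and type I error is intact.
- *Pooling dilutes the effect.* If the app did less in GI recruits (effect of 0-10 points, GI share 10-50%), power would fall to between 0.28 and 0.77. Nothing in the documents indicates a smaller GI effect, and neither adjustment nor stratification would recover that loss.

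**Stratification may come too late.** Section 5d places enrolment in years 3-4 of a study begun in September 2015, and the document is dated 8/16/2019. On that schedule enrolment is nearly over.

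**Conclusion.** The point holds as a modest matter of efficiency and clarity. The timing sentence in section 1 conflicts with sections 3 and 5f. Setting, known before assignment, is left to a screen that, on its natural reading, responds to chance imbalance.

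Replacing the screen with a fixed term is worth about 1-2 points of power at an assumed 20-30 point uptake gap, about 4 points at a 40-point gap and nothing at 10 points. This assumes a GI share of 40-50% and a common odds ratio. The primary comparison remains valid without the change. The case for making it is that it costs almost nothing, removes a data-dependent choice and gives a planned description by setting.

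**What to change.** 1. In section 5h, prespecify recruitment setting as a fixed term in the primary logistic model, outside the p ≤ 0.15 screen. Define its levels, including how West 147th Street is coded, because section 3 does not say whether its visits are primary care or GI.
2. Add a table of uptake by arm within primary care and GI recruits, labelled descriptive because interaction power is low.
3. Reconcile the app-timing sentence in section 1 with sections 3 and 5f.
4. Optionally, stratify the remaining assignments by setting if enough enrolment is left. Little is lost if this is not done.

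The cost is one recorded variable, one model term, one table and one corrected sentence, with no added participants or visits. The small downside is an odds ratio conditional on setting, which the report should state.

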Throughout the study, quantitative survey data will be collected. The survey data will be scanned and uploaded on our Department's secure internet server (J drive). The hard copies of the surveys will be stored in a locked filing cabinet in the CAM building. Each participant's data will be de-identified and assigned an anonymous ID number. A "cross-over" file matching ID number with participant identifying information (name, address and phone number) will be maintained and stored separately on our department's secured and encrypted intranet server. Only study personnel will have access to the crossover file.

 Mount Sinai	Protocol Name:	Internet-based Motivational Interviewing for Colonoscopy in African Americans
	Principal Investigator:	[name]
	Primary Contact Name/Contact Info:	[name], [contact] ,
	Date Revised:	8/16/19
	Study Number:	GCO# 14-0275 IF# HS#

CERNER Data:

In addition, as part of the RCT, we will first obtain the CERNER list to identify the Black/African American patients who are age eligible or CRC screening and are scheduled for a primary care or GI appointment that day. We will then access EMR to identify whether the patient may be eligible for a screening colonoscopy (has not had a recent screening colonoscopy procedure in the EMR). We have requested a HIPAA waiver. We will then alert the physicians and patient navigators of the patients who may be eligible or our study. The CERNER list will be destroyed at the end of each recruitment shift.

App Engagement Data:

We will record participants' engagement with e-Motivate. The e-Motivate will be linked to an electronic database that will be entirely anonymous and will only record the participants' overall engagement (e.g. responses to the exercises, amount of time spent on each exercise, etc.). The database will initially be stored on the AppLab's encrypted server. The anonymous dataset will then be sent to the Mount Sinai investigative team.

Outcome Data:

Six months following the initial visit, we will check the medical records of all consented participants in Phase II to obtain outcome data (e.g., colonoscopy completion status, prep quality, # of cancellations/rescheduled appointments/no-shows, receipt of PN/care coordination). The medical information will be de-identified and stored on a password protected file on Mount Sinai's intranet server.

DATA ANALYSES

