Analysis of Power: We are proposing a sample of 200 participants (100 in each treatment arm) and setting alpha equal to 0.05. In our pilot study, the MI condition was associated with 71.4% (20/28) screening uptake compared to 52.0% (13/25) for the control condition. Based on these results, we are hypothesizing that approximately 71.4% of participants in e-Motivate condition will complete the colonoscopy, compared to approximately 52% of the participants in the control condition. Based on these projections, power is equal to 0.83. Of note, for the proposed study, the control condition will be a print brochure. Previous research suggests that a print brochure produces comparable CRC screening rates (52.0%-53.5%) to our pilot study's attention control condition (52.0%).

i) Provisions to Monitor the Data to Ensure the Safety of Subjects

Part I: Elements of a Data and Safety Monitoring Plan

1. List the name(s) of the individual(s) at the Mount Sinai School of Medicine (MSSM) who will be responsible for data and safety monitoring of this study. For each individual, indicate their role, name, title, and department information.

MSSM Principal Monitor:

Check One: PI: Team Member: Independent:

Last Name: [name]

First Name: [name]

Academic Title: Instructor

Department: Oncological Sciences

Mailing Address: [name]

[contact]

[contact]

E-mail: [contact]

MSSM Additional Monitor:

Check One: PI: Team Member: Independent:

Last Name: [name]

First Name: [name]

Academic Title: Professor

Department: Oncological Sciences

Mailing Address: [name]

[contact]

 Mount Sinai	Protocol Name:	Internet-based Motivational Interviewing for Colonoscopy in African Americans
	Principal Investigator:	[name]
	Primary Contact Name/Contact Info:	[name], [contact] ,
	Date Revised:	8/16/19
	Study Number:	GCO# 14-0275 IF# HS#

[contact]
E-mail: [contact]

2. Justify your choice of principal monitor in terms of the assessed risk to the research subject's health and wellbeing. In high risk studies when the principal monitor is independent of the study staff, indicate the individual's credentials, relationship to the PI, and the rationale for selection.

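### Prior colonoscopy is reviewed before recruitment but not named as a study variable; fixing it as a covariate in the primary model would be a cheap, optional gain in precision and pre-specification.

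*Combined protocol and SAP*

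**What the plan says.** - **Eligibility, 5(b).** Besides self-identified race, the criteria are "2) received a referral for a screening colonoscopy; and 3) English speaking". The exclusions are sensory impairment and Phase I participation. Neither list mentions an earlier colonoscopy.
- **Pre-screening, 5(f) RCT Procedures and 5(h) CERNER Data.** On each recruitment day the research assistants review "race, age, and previous colonoscopy history" and alert providers to patients who may be eligible. The record check asks only whether there has been a recent screening colonoscopy, so an older one is no bar.
- **Retention, 5(h) CERNER Data.** "The CERNER list will be destroyed at the end of each recruitment shift". Nothing says that colonoscopy history is carried into the study data. The items named for baseline collection (5(e)) and for the six-month chart review (5(f), 5(h)) do not include it.
- **Primary model, 5(h) Data Analyses.** Logistic regression with treatment, any identified covariates and any significant moderators. No covariate is fixed in advance. At p ≤ 0.15, "any consistent pattern of correlation for any of the covariates would suggest their inclusion in the primary data analysis model". The moderators named in Exploratory Aim 2b are demographics and Internet fluency or use.

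**The concern.** The primary outcome is completion of a colonoscopy. Whether a patient has completed one before is close to a baseline version of that outcome, so it is a natural candidate for adjustment. The team already looks at it, yet the plan neither records it as a study variable nor gives it a place in the model.

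The covariate screen does not fill the gap. The sentence before it describes contingency tables and t-tests between the two groups. Read that way, the screen responds to chance imbalance and not to prognostic value, so a balanced but strong predictor would usually be left out. Whether the covariate enters would also depend on the data. At stake are some precision in the treatment comparison and a firmer specification of the primary model.

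**Working it through.** **Inputs from the plan (Analysis of Power).** 100 participants per arm; "setting alpha equal to 0.05" (sidedness not stated, two-sided assumed); "approximately 71.4% of participants in e-Motivate condition will complete the colonoscopy", "compared to approximately 52% of the participants in the control condition"; stated power 0.83.

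**1. The plan's own figure.**
- SE of the difference, unpooled: √(0.714×0.286/100 + 0.52×0.48/100) = 0.0674.
- Pooled-variance test, mean rate 0.617: Φ[(0.194 − 1.96×√(2×0.617×0.383/100)) / 0.0674] = 0.810.
- Unpooled test: Φ(0.194/0.0674 − 1.96) = 0.821.
- Wald test of the log odds ratio, which matches the planned logistic model: log OR = 0.835, SE = √(1/(100×0.714×0.286) + 1/(100×0.52×0.48)) = 0.298, power 0.799.

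The stated 0.83 is reproduced to within about 2 points by the first two methods. The logistic Wald figure of 0.799 is the baseline for step 2.

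**2. Power with a fixed binary covariate.** The share of repeat screeners and their odds ratio (OR) with uptake are assumptions. For each pair, the intercept and treatment coefficient b were solved so that the overall rates stay at 52% and 71.4%. The SE of b comes from the expected information matrix Σ n·p(1−p)·vvᵀ, with v = (1, treatment, prior colonoscopy). Power = Φ(b/SE − 1.96).

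| OR with uptake | Power, share 20% | Power, share 50% | Gain over 0.799 (points) |
|---|---|---|---|
| 1 | 0.799 | 0.799 | 0 |
| 1.5 | 0.801 | 0.802 | 0.2–0.3 |
| 2 | 0.804 | 0.808 | 0.5–0.9 |
| 3 | 0.811 | 0.822 | 1.2–2.3 |
| 4 | 0.817 | 0.834 | 1.8–3.5 |
| 4.5 | 0.820 | 0.839 | 2.1–4.0 |

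Example, share 50% and OR 4.5: control uptake is 34% in first-timers and 70% in repeat screeners; b = 0.946, SE = 0.321, power 0.839. The treatment OR conditional on prior colonoscopy is then exp(0.946) = 2.58, against 2.30 unadjusted.

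**3. The p ≤ 0.15 screen, read as a between-arm test.** In 10,000 simulated trials per scenario (share 20% or 50%, OR 1 to 3), it selected prior colonoscopy in about 13–15% of trials. Power was 0.809–0.818 unadjusted, 0.811–0.820 with the screen and 0.811–0.839 with the fixed term.

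**4. Chance imbalance.** The SD of the between-arm difference in the share g of repeat screeners is √(2g(1−g)/100): 5.7 points at g = 0.2 and 7.1 points at g = 0.5. A 10-point imbalance moves the crude uptake difference by about 1.0 point (OR 1.5) to 3.3 points (OR 4). For comparison, the SE of that difference is 6.7 points and the planned effect is 19.4 points.

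**5. Imperfect charts.** If charts captured 60% of earlier procedures (an assumption), simulated adjusted power falls from 0.830 to 0.816 (share 40%, OR about 3.5) and from 0.852 to 0.824 (share 50%, OR about 4.5).

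**The case against.** The strongest reply is that this is one choice of covariate in a randomised trial whose primary test is valid without it. That stands. Chance imbalance is part of the sampling error that the test already allows for, and the gain is small unless the association is strong.

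A second reply is that the existing rule may already cover the variable. If the wording about a pattern of correlation means correlation with the outcome, the screen would pick up a strong predictor: over 99% of simulated trials at odds ratios of about 3.5 to 4.5. If it means a difference between arms, it would still catch the larger imbalances, above about 10 points at a 50% share (1.44 × 7.1). Both readings require the variable to be recorded, which the plan does not say, and both leave inclusion to the data. The reply stands only in part.

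Four stronger readings are tempting, and the documents do not support them:

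- **The history is lost when the list is destroyed.** The list serves to find scheduled patients. The history sits in the electronic record, and charts of all consented participants are reopened at six months.
- **The baseline questionnaire omits it.** 5(f) does not itemise that questionnaire, and Internet use is to be explored although 5(e) does not list it. A prior-screening item is unstated, not shown to be absent.
- **The app itself relies on prior colonoscopy.** 5(f) lists a video on previous success among general motivational exercises and does not say that the success is a colonoscopy.
- **The comparison is biased or the trial underpowered without the covariate.** Randomisation protects against systematic bias, and the power statement contains no covariate that could invalidate it.

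**Conclusion.** The point holds as an optional improvement in precision and pre-specification. The plan admits both first-time and repeat screeners, has staff review colonoscopy history, does not say that the history is kept, and fixes no covariate for the primary model.

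The size is modest. The upper end of the gain, about 4 points, needs half the participants to be repeat screeners and an odds ratio of about 4.5. The required sample size does not change materially. That prior colonoscopy predicts uptake is plausible but undocumented. If it does not, step 2 shows no loss of power from including it.

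**What to change.** Before any outcome analysis, make two additions.

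1. **Chart-review form.** Add one field, prior colonoscopy before assignment (yes/no), taken from the electronic record at the six-month review and counting only procedures dated before assignment. Use this one source for every participant. The pre-recruitment look-up would not do, because patients may also enter through telephone contact or when no research assistant is on site. A chart field also reaches those already enrolled: the timeline puts enrolment in Years 3–4 of a study that began in September 2015, so it may have been largely complete by the August 2019 revision. Self-report may be kept as a supplement, but should not define the covariate for some participants only.
2. **Analysis of Primary Outcome.** State that this term is in the primary logistic model whatever the p ≤ 0.15 screen shows, and that the resulting treatment odds ratio is conditional on it.

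The cost is one extracted field, one sentence or two in the analysis section, one degree of freedom, and a treatment odds ratio that is no longer the crude one.
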